7.3.1.11.2 Investigation of Hemolytic Potential

Investigation of the hemolytic potential of any INTERCEPT RBC-specific antibodies found in the ReCePI study will be conducted by a Central Laboratory according to the document titled “Evaluation of Reactivity with INTERCEPT RBC” provided to the sites and filed in the Investigator Site File and the protocol in APPENDIX 2. Patient samples will be managed using the supplemental instructions for patient and laboratory sample management for studies involving INTERCEPT Blood System for RBCs when a reactive S-303 result is obtained (S-303 Reactive Samples: Management of Patients and Samples; REF 01606) Possible studies may include:

- Antibody specificity via inhibition studies (inhibited by soluble acridine or not)
- Antibody characterization:
- Immunoglobulin isotype and IgG subclass (IgM, IgG_{1, 2, 3 or 4})
- Antibody titer
- Persistence and titer over time
- Thermal spectrum and phase of reaction
- Complement-mediated in vitro hemolysis
- Investigation of concurrent antibodies to intrinsic RBC allo-antigens
- Monocyte Monolayer Assay for clinical significance (Arndt and Garratty 2004)

Cerus Corporation

Title: A Randomized, Double-Blinded, Controlled, Parallel Group, Non-inferiority, Phase III Study to Evaluate the Efficacy and Safety of the INTERCEPT Blood System for Red Blood Cells in Patients undergoing Complex Cardiac Surgery Procedures (the ReCePI study)

7.3.1.12 Abnormal Test Findings

The criteria for determining whether an abnormal objective test finding should be reported as an adverse event are as follows:

- Test result is associated with accompanying symptoms, and/or
- Test result requires additional diagnostic testing or medical/surgical intervention, and/or
- Test result leads to a change in trial dosing or discontinuation from the study participation, significant additional concomitant drug treatment, or other therapy, and/or
- Test result is considered to be an adverse event by the Investigator or Sponsor.

Merely repeating an abnormal test, in the absence of any of the above conditions, does not constitute an adverse event. Any abnormal test result that is determined to be an error does not require reporting as an adverse event.

7.3.2 Methods and Timing of Safety Parameters

The use of intravenous radiographic contrast media will be documented starting 7 days prior to surgery, as will details related to the specific surgical procedure (type of procedure, start and end times), RBC components transfused, all other blood components transfused, estimated blood loss from the surgical procedure, concomitant medications, intraoperative cell recovery and reinfusion, hemodilution, and nadir temperature. Additionally, daily estimated blood loss from chest tube(s) and from other sources, and day of chest tube removal will be recorded. Safety events (TRs, AEs and SAEs) will be documented on a daily basis during the acute transfusion support period (through Day 7).

Subjects will continue to be monitored through a post-surgical follow-up period for up to 28 days after the last study transfusion, or death, whichever occurs first. During this period, subjects will be monitored for safety events. Blood samples for laboratory studies, DAT/IAT and for antibodies specific to INTERCEPT RBC- associated antigens will be obtained at 28 ± 3 days after the last study transfusion and at end of study.

All samples obtained for determination of human leukocyte antigen (HLA) will be stored for up to 1 year after the study has completed.

Cerus Corporation

Title: A Randomized, Double-Blinded, Controlled, Parallel Group, Non-inferiority, Phase III Study to Evaluate the Efficacy and Safety of the INTERCEPT Blood System for Red Blood Cells in Patients undergoing Complex Cardiac Surgery Procedures (the ReCePI study)

7.4 REPORTING PERIOD

All safety events will be collected from the start of surgery or the start of the first study transfusion (whichever is first) through 28 days after the last study transfusion or death, whichever is first.

Vital status and need for RRT of all subjects will be collected at 30 days after the end of surgery and at the end of study visit (Day 75 ±15 days).

Blood sample for assessment of sCr will be collected on post-operative day 2 (at 48 ± 4 hours post end of surgery) for the primary endpoint. For non-transfused subjects, a blood sample for sCr will be drawn at 48 ± 4 hours post-surgery.

Blood samples for assessment of INTERCEPT RBC-specific antibody, HLA antibodies and chemistry and hematology laboratory studies at 28±3 days after the last study transfusion.

Blood samples for assessment of INTERCEPT RBC-specific antibody will also be obtained 75 ±15 days after the last study transfusion.

7.5 RECORDING AND REPORTING ADVERSE EVENTS**7.5.1 Assessing Severity of an Adverse Event**

The Investigator will assess the severity of each adverse event based on the NCI Common Terminology Criteria for Adverse Events (CTCAE) (APPENDIX 4) and summarized in **Table 7.4**.

Cerus Corporation

Title: A Randomized, Double-Blinded, Controlled, Parallel Group, Non-inferiority, Phase III Study to Evaluate the Efficacy and Safety of the INTERCEPT Blood System for Red Blood Cells in Patients undergoing Complex Cardiac Surgery Procedures (the ReCePI study)

Table 7.4 Severity Assessment of Adverse Events

Grade 1: Mild asymptomatic or mild symptoms; clinical or diagnostic observations only; intervention not indicated.
Grade 2: Moderate; minimal, local or noninvasive intervention indicated; limiting age-appropriate instrumental ADL
Grade 3: Severe or medically significant but not immediately life threatening; hospitalization or prolongation of hospitalization indicated; disabling; limiting self-care ADL
Grade 4: Life-threatening consequences; urgent intervention indicated.
Grade 5: Death related to AE.

Link to NCI CTCAE 5.0:

https://ctep.cancer.gov/protocoldevelopment/electronic_applications/docs/CTCAE_v5_Quick_Reference_8.5x11.pdf ([APPENDIX 4](#))

Note the distinction between the severity and the seriousness of an adverse event. A severe event is not necessarily a serious event. For example, a headache may be severe (interferes significantly with patient's usual function) but would not be classified as serious unless it met one of the criteria for serious adverse events. Consistency between severity and seriousness assessments should be ensured by the Investigator.

7.5.2 Assessing Seriousness of an Adverse Event

The Investigator will assess if an AE resulted in any one or more of the following outcomes that result in classification of the event as an SAE: death, a life-threatening event (results in an immediate risk of death from the reaction as it occurred), inpatient hospitalization or prolongation of existing hospitalization, a persistent or significant disability/incapacity, a congenital anomaly/birth defect, or another important medical event (Section 7.3.1.2).

7.5.3 Assessing Causality of an Adverse Event

The Investigator's assessment of causality must be provided for all adverse events (serious and non-serious). An Investigator's causality assessment is the determination of whether there exists a reasonable possibility that the investigational product caused or contributed to an adverse event. If the Investigator does not know whether or not investigational product caused the event, then the event will be handled as "possibly related to investigational product" for reporting purposes.

Adverse events assessed by the Investigator to be related (possible, likely/probable) to the investigational product also must be evaluated as a Transfusion Reaction and classified per the CDC NHSN Hemovigilance Protocol ([APPENDIX 3](#)).

The standard nomenclature for defining the causal relationship between an AE and the

Cerus Corporation

Title: A Randomized, Double-Blinded, Controlled, Parallel Group, Non-inferiority, Phase III Study to Evaluate the Efficacy and Safety of the INTERCEPT Blood System for Red Blood Cells in Patients undergoing Complex Cardiac Surgery Procedures (the ReCePI study)

blinded study product transfused is listed in **Table 7.5**.

Table 7.5 Relationship between Investigational Product and Adverse Events

Imputability Level	Explanation
Excluded	When there is conclusive evidence beyond reasonable doubt that the adverse event can be attributed to alternative causes
Unlikely	When the evidence is clearly in favor of attributing the adverse event to causes other than the study transfusion
Possible	When the evidence is indeterminate for attributing the adverse event to the study transfusion or an alternate cause
Likely/Probable	When the evidence is clearly in favor of attributing the adverse event to the study transfusion
Certain/Definite	When there is conclusive evidence beyond reasonable doubt that the adverse event can be attributed to the study transfusion

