4 INVESTIGATIONAL PLAN

4.1 ENDPOINTS

4.1.1 Primary Endpoints

The primary efficacy endpoint is the proportion of patients, who have received at least one study transfusion with a diagnosis of renal impairment defined as:

- Any raised sCr level, occurring after transfusion of a study RBC, of ≥ 0.3 mg/dL (or 26.5 μ mol/L) from the pre-surgery baseline within 48 ± 4 hours of the end of surgery.

If any subject meets this criterion before receiving a study transfusion, that particular event will not be included in the primary endpoint analysis. The treatment comparison for the primary efficacy endpoint will be assessed by a non-inferiority test (Test–Control) with a non-inferiority margin of 50% increase from the Control rate and two-sided 0.05 alpha level. Patients who receive a study transfusion but die within 48 hours after surgery will be included in the mITT analysis but excluded from the per protocol analysis.

The primary safety endpoints are:

- Proportion of patients with any treatment-emergent adverse events (TEAEs) possibly, probably or definitely related to study RBC transfusion through 28 days after the last study transfusion; and
- Proportion of patients with treatment-emergent antibodies with confirmed specificity to INTERCEPT RBCs by end of study (i.e., 75 ± 15 days after the last study transfusion).

TEAEs by definition will comprise all untoward medical events occurring after the start of the first study RBC transfusion and during the study (i.e., adverse events, serious adverse events, unanticipated adverse device effects, TRs and within 28 days post last study RBC transfusion). The primary safety endpoint is focused on possibly, probably or definitely related adverse events to the study RBC transfusion, because these patients have many adverse events which are unrelated to study RBC transfusion.

Cerus Corporation

Title: A Randomized, Double-Blinded, Controlled, Parallel Group, Non-inferiority, Phase III Study to Evaluate the Efficacy and Safety of the INTERCEPT Blood System for Red Blood Cells in Patients undergoing Complex Cardiac Surgery Procedures (the ReCePI study)

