7.3.1.10 Definition of Transfusion Reaction

A transfusion reaction is defined as an undesirable response or effect in a patient temporally associated with and possibly, probably or definitely related to the administration of blood or blood components. The current version of the CDC NHSN Hemovigilance Protocol definitions must be used when recording transfusion reaction

Cerus Corporation

Title: A Randomized, Double-Blinded, Controlled, Parallel Group, Non-inferiority, Phase III Study to Evaluate the Efficacy and Safety of the INTERCEPT Blood System for Red Blood Cells in Patients undergoing Complex Cardiac Surgery Procedures (the ReCePI study)

terms in this study ([APPENDIX 3](#)).

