**Adverse Reaction Case Classification Criteria Tables****Transfusion-associated circulatory overload (TACO)**

Case Definition	Severity	Imputability
Definitive: New onset or exacerbation of 3 or more of the following within 6 hours of cessation of transfusion: 
 • Acute respiratory distress (dyspnea, orthopnea, cough) • Elevated brain natriuretic peptide (BNP) • Elevated central venous pressure (CVP) • Evidence of left heart failure • Evidence of positive fluid balance • Radiographic evidence of pulmonary edema 	Non-severe: Medical intervention (e.g. symptomatic treatment) is required but lack of such would not result in permanent damage or impairment of a bodily function. Severe: Inpatient hospitalization or prolongation of hospitalization is directly attributable to the adverse reaction, persistent or significant disability or incapacity of the patient occurs as a result of the reaction, or a medical or surgical intervention is necessary to preclude permanent damage or impairment of a body function. Life-threatening: Major intervention required following the transfusion (e.g. vasopressors, intubation, transfer to intensive care) to prevent death. Death: The recipient died as a result of the adverse transfusion reaction. Death should be used if death is possibly, probably or definitely related to transfusion. If the patient died of a cause other than the transfusion, the severity of the reaction should be graded as appropriate given the clinical circumstances related to the reaction. Not Determined: The severity of the adverse reaction is unknown or not stated.	Definite: No other explanations for circulatory overload are possible. Probable: Transfusion is a likely contributor to circulatory overload AND EITHER The patient received other fluids as well OR The patient has a history of cardiac insufficiency that could explain the circulatory overload, but transfusion is just as likely to have caused the circulatory overload. Possible: The patient has a history of pre-existing cardiac insufficiency that most likely explains circulatory overload.
Probable: N/A		OPTIONAL
Possible: N/A		Doubtful: Evidence is clearly in favor of a cause other than the transfusion, but transfusion cannot be excluded.
		Ruled Out: There is conclusive evidence beyond reasonable doubt of a cause other than the transfusion.
		Not Determined: The relationship between the adverse reaction and the transfusion is unknown or not stated.

Cerus Corporation

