Title: A Randomized, Double-Blinded, Controlled, Parallel Group, Non-inferiority, Phase III Study to Evaluate the Efficacy and Safety of the INTERCEPT Blood System for Red Blood Cells in Patients undergoing Complex Cardiac Surgery Procedures (the ReCePI study)

NHSN Biovigilance Component
Hemovigilance Module Surveillance Protocol v2.5.2
www.cdc.gov/nhsn

Transfusion-associated dyspnea (TAD)

Case Definition	Severity	Imputability
Definitive: Acute respiratory distress occurring within 24 hours of cessation of transfusion AND Allergic reaction, TACO, and TRALI definitions are not applicable.	Non-severe: Medical intervention (e.g. symptomatic treatment) is required but lack of such would not result in permanent damage or impairment of a bodily function. Severe: Inpatient hospitalization or prolongation of hospitalization is directly attributable to the adverse reaction, persistent or significant disability or incapacity of the patient occurs as a result of the reaction, or a medical or surgical intervention is necessary to preclude permanent damage or impairment of a body function.	Definite: Patient has no other conditions that could explain symptoms. Probable: There are other potential causes that could explain symptoms, but transfusion is the most likely cause. Possible: Other present causes are most likely, but transfusion cannot be ruled out.
Probable: N/A	Life-threatening: Major intervention required following the transfusion (e.g. vasopressors, intubation, transfer to intensive care) to prevent death.	OPTIONAL
Possible: N/A	Death: The recipient died as a result of the adverse transfusion reaction . Death should be used if death is possibly, probably or definitely related to transfusion. If the patient died of a cause other than the transfusion, the severity of the reaction should be graded as appropriate given the clinical circumstances related to the reaction. Not Determined: The severity of the adverse reaction is unknown or not stated.	Doubtful: Evidence is clearly in favor of a cause other than the transfusion, but transfusion cannot be excluded. Ruled Out: There is conclusive evidence beyond reasonable doubt of a cause other than the transfusion. Not Determined: The relationship between the adverse reaction and the transfusion is unknown or not stated.

Cerus Corporation

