**Acute hemolytic transfusion reaction (AHTR)**

Note: Report hemolytic reactions resulting from immune or non-immune causes, including when the recipient is intentionally transfused with incompatible blood components.

Case Definition	Severity	Imputability

Definitive: Occurs during, or within 24 hours of cessation of transfusion with new onset of ANY of the following signs/symptoms:
 
 • Back/flank pain • Chills/rigors • Disseminated intravascular coagulation (DIC) • Epistaxis • Fever • Hematuria (gross visual hemolysis) • Hypotension • Oliguria/anuria • Pain and/or oozing at IV site • Renal failure 
AND 2 or more of the following:
 
 • Decreased fibrinogen • Decreased haptoglobin • Elevated bilirubin • Elevated LDH • Hemoglobinemia • Hemoglobinuria • Plasma discoloration c/w hemolysis • Spherocytes on blood film 
AND EITHER
 
(IMMUNE-MEDIATED) Positive direct antiglobulin test (DAT) for anti-IgG or anti-C3
 
AND Positive elution test with alloantibody present on the transfused red blood cells
 
OR
 
(NON-IMMUNE MEDIATED) Serologic testing is negative, and physical cause (e.g., thermal, osmotic, mechanical, chemical) is confirmed.
 
Probable: Meets signs and symptoms criteria for acute hemolysis.
 
AND EITHER
 
(IMMUNE MEDIATED) Physical cause is excluded but serologic evidence is not sufficient to meet definitive criteria
 
OR
 
(NON-IMMUNE MEDIATED) Physical cause is suspected and serologic testing is negative.
	
Non-severe: Medical intervention (e.g., symptomatic treatment) is required but lack of such would not result in permanent damage or impairment of a bodily function.
 
Severe: Inpatient hospitalization or prolongation of hospitalization is directly attributable to the adverse reaction, persistent or significant disability or incapacity of the patient occurs as a result of the reaction, or a medical or surgical intervention is necessary to preclude permanent damage or impairment of a body function.
 
Life-threatening: Major intervention required following the transfusion (e.g., vasopressors, intubation, transfer to intensive care) to prevent death.
 
Death: The recipient died as a result of the adverse transfusion reaction. Death should be used if death is possibly, probably or definitely related to transfusion. If the patient died of a cause other than the transfusion, the severity of the reaction should be graded as appropriate given the clinical circumstances related to the reaction.
 
Not Determined: The severity of the adverse reaction is unknown or not stated.
	
Definite: ABO or other allotypic RBC antigen incompatibility is known OR Only transfusion-related (i.e., immune or non-immune) cause of acute hemolysis is present.
 
Probable: There are other potential causes present that could explain acute hemolysis, but transfusion is the most likely cause.
 
Possible: Other causes of acute hemolysis are more likely, but transfusion cannot be ruled out.
 
OPTIONAL
 
Doubtful: Evidence is clearly in favor of a cause other than the transfusion, but transfusion cannot be excluded.
 
Ruled Out: There is conclusive evidence beyond reasonable doubt of a cause other than the transfusion.
 
Not Determined: The relationship between the adverse reaction and the transfusion is unknown or not stated.

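### Section 7.5.3 triggers transfusion reaction evaluation from an incomplete list of Table 7.5 ratings, which omits definite events and can miss some that NHSN rates as possible

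*Protocol*

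**What the plan says.** Three parts of the protocol bear on this.

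- **Endpoints.** The first primary safety endpoint (4.1.1) is the proportion of patients with treatment-emergent adverse events "possibly, probably or definitely related to study RBC transfusion through 28 days after the last study transfusion". Transfusion reactions, as defined by the CDC NHSN Hemovigilance Module, are a separate safety endpoint (4.1.2). Section 7.3.1.10 makes NHSN definitions mandatory for recording transfusion reaction terms and describes a reaction as "temporally associated with and possibly, probably or definitely related to the administration of blood or blood components".
- **Relatedness scale.** The investigator rates each adverse event on Table 7.5: Excluded, Unlikely, Possible, Likely/Probable or Certain/Definite. Possible applies "When the evidence is indeterminate for attributing the adverse event to the study transfusion or an alternate cause". Unlikely applies "When the evidence is clearly in favor of attributing the adverse event to causes other than the study transfusion".
- **Routing rule.** Section 7.5.3 then says: "Adverse events assessed by the Investigator to be related (possible, likely/probable) to the investigational product also must be evaluated as a Transfusion Reaction", with classification under the NHSN protocol reproduced in Appendix 3.

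**The concern.** The routing sentence decides which events a site must take through NHSN classification. It has two faults.

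First, its list of qualifying ratings stops at Likely/Probable. Followed literally, it does not require NHSN evaluation of the events most firmly attributed to the study transfusion.

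Second, it uses the Table 7.5 rating as the trigger for an endpoint that rests on NHSN criteria. For several named reactions, the lowest NHSN level that counts is wider than Possible in Table 7.5. An event can therefore meet the NHSN criteria without triggering the mandatory evaluation.

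Completeness and consistency between sites of the transfusion reaction endpoint are at stake. This population is exposed because competing explanations, such as pre-existing cardiac insufficiency, are common in cardiac surgery.

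**Working it through.** The protocol gives no rate, hypothesis or margin for this endpoint, so there is no figure to reproduce. The check sets the texts side by side.

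**Step 1. Which ratings count as related?**

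| Place | Possible | Probable | Definite |
|---|---|---|---|
| 4.1.1, primary safety endpoint | yes | yes | yes |
| 7.3.1.10, transfusion reaction definition | yes | yes | yes |
| Table 7.5, levels available | yes | yes | yes |
| 7.5.3, routing sentence | yes | yes | **absent** |

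The routing sentence is the only one of the four without the definite level. A definite event still counts in the primary safety endpoint. What the literal rule drops is the requirement to classify it under NHSN.

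**Step 2. What does Possible mean on each scale?**

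| Source | Content of Possible |
|---|---|
| Table 7.5 | "When the evidence is indeterminate for attributing the adverse event to the study transfusion or an alternate cause" |
| Appendix 3, circulatory overload (TACO) | "The patient has a history of pre-existing cardiac insufficiency that most likely explains circulatory overload" |
| Appendix 3, dyspnea (TAD); same wording for febrile reaction (FNHTR) | "Other present causes are most likely, but transfusion cannot be ruled out" |
| Appendix 3, acute hemolytic reaction (AHTR) | "Other causes of acute hemolysis are more likely, but transfusion cannot be ruled out" |

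Table 7.5 treats Possible as evidence that does not settle the matter. The four reaction-specific rows also admit events where another cause is judged more likely or most likely.

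**Step 3. Follow one event through.** A patient with pre-existing cardiac insufficiency meets the case definition for circulatory overload, and the investigator thinks the cardiac history most likely explains it.

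1. Under the NHSN row the event is Possible.
2. On Table 7.5 the investigator may reasonably choose Unlikely, if the evidence is judged clearly to favor the cardiac cause.
3. Unlikely is not in the routing list, so section 7.5.3 does not require NHSN evaluation.
4. Another site could rate the same event Possible on Table 7.5, and evaluation would then be mandatory.

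**Step 4. How far does the overlap extend?** Three comparisons limit it.

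- The NHSN level Doubtful, which is optional to report, is worded almost like Unlikely in Table 7.5. Events on which both scales see clear evidence for another cause are treated alike.
- The NHSN generic scale for Other or Unknown reactions matches Table 7.5 closely. The mismatch lies in the reaction-specific rows, not in the NHSN scale as a whole.
- NHSN Possible for acute lung injury (TRALI) asks only for evidence of another listed cause, such as cardiopulmonary bypass. It does not ask that this cause be more likely. On Table 7.5 that reads naturally as indeterminate, hence Possible.

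**Step 5. Direction of the effect.** Let f be the share of NHSN-qualifying reactions missed, equal in both arms. Each observed rate is the true rate times (1 − f), so the absolute difference also shrinks by (1 − f) and the rate ratio is unchanged. With assumed rates of 10% and 20%, which are not from the protocol, the 10.0-point difference becomes:

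- f = 0.25: 10.0 × 0.75 = 7.5 points
- f = 0.50: 10.0 × 0.50 = 5.0 points
- f = 0.75: 10.0 × 0.25 = 2.5 points

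This shows direction only. The protocol gives no basis for f or for either rate.

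**The case against.** The strongest reply is that the rule sets a minimum and bars nothing. Transfusion reactions are assessed and documented in their own right alongside adverse events (6.1.2, 7.3.2, 7.5.5), with no relatedness condition stated there. All treatment-emergent adverse events and serious adverse events are also reported regardless of relatedness (4.1.2). Section 7.5.3 handles unknown causality as possibly related and asks whether the product may have caused or contributed to the event; both push doubtful cases toward a qualifying rating. The bracket can be read as a loose gloss on the word related, and few sites would exempt a definite reaction.

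Most of this stands, and it defeats three stronger readings that a reader might infer:

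- **That the affected events are never counted.** They stay in the overall adverse event summaries and can still be recorded as transfusion reactions.
- **That Table 7.5 is the wrong scale for the primary safety endpoint.** That endpoint concerns relatedness to study red cells, and section 7.5.3 assigns that judgment to Table 7.5. NHSN governs transfusion reactions.
- **That every on-pump lung injury is lost.** Bypass does hold NHSN imputability at Possible, but step 4 shows that such a case fits Possible on Table 7.5 as well.

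The reply does not remove the narrower point. No passage says that screening for transfusion reactions is independent of the Table 7.5 rating, and the only explicit instruction ties the two together. The unknown-causality default helps an investigator who does not know, not one who judges another cause clearly favored.

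**Conclusion.** The point holds in a limited form. The missing definite level is a plain contradiction with 4.1.1, 7.3.1.10 and Table 7.5. The dependence on Table 7.5 is a real but narrow weakness, confined to reaction-specific NHSN rows such as those for circulatory overload, dyspnea, febrile and acute hemolytic reactions.

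The likely consequence is uneven or low ascertainment of transfusion reactions. Operating room, surgical and ICU staff are blinded (4.3), so the loss should be similar in both arms. It would lower both rates and shrink an absolute difference, without favoring one product by design.

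The size cannot be estimated from the protocol. A reader might assume that 2% to 6% of patients have such reactions and obtain 0.02 × 292 = 5.8 to 0.06 × 292 = 17.5 patients. That range rests wholly on the assumed rate and on every such event being rated differently on the two scales. Nor do the documents show that a treatment difference would be hidden: the protocol plans descriptive safety summaries (8.1.2), and some events left out may truly have other causes.

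**What to change.** In section 7.5.3:

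1. Add certain/definite to the bracket in the routing sentence.
2. State that any adverse event suspected of meeting an NHSN case definition is evaluated, and given an NHSN imputability level for the transfusion reaction endpoint, whatever its Table 7.5 rating.
3. Keep Table 7.5, as relatedness to study red cells, as the scale for the primary related-event endpoint.
4. Require the two ratings to be reconciled when they differ for the same event.

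NHSN imputability should not replace Table 7.5 in the primary safety endpoint. It covers transfusion of any blood component, and patients may also receive other components and non-study red cells (Table 7.1c). The substitution could count reactions to those products as related to study red cells and would change the endpoint.

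The cost is protocol and eCRF guidance wording, plus a few more adverse events classified on an existing form.
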